6.3 Treatment

Patients will be treated on a linear accelerator equipped with cone beam CT image-guidance, or on a Cyberknife platform. Daily image guidance must be performed and confirmed by a physician or medical physicist before each treatment. If the shift exceeds 7mm, a second confirmatory image acquisition using the image guidance platform will need to be performed to confirm that residual error is <3mm. Residual error >3mm requires repositioning of the patient. Radiation fractions will be given with at least 40 hours between fractions and typically be delivered every other day (e.g. M, W, F, M, W). Twice weekly fractions are also acceptable (e.g. M, Th, M, Th, M). Total treatment time should be between 10-18 days.

6.4 Duration of Follow Up

Patients will be followed for toxicity for 1 year after treatment has been discontinued or until death, whichever occurs first. Following completion of this period of follow-up on-study patients will then be followed per standard of care as detailed below.

The clinical course of each event will be followed until resolution, stabilization, or until it has been determined that the study treatment or participation is not the cause. Serious adverse events that are still ongoing at the end of the study period will necessitate follow-up to determine the final outcome.

Patients will be followed for one year after SBRT. All patients will be seen at 0.5, 3, 6, 9, 12 months after SBRT. At the three month visit, a post-SBRT PET/CT will be obtained to assess for disease response. CT of the neck and chest (preferably with contrast barring allergies or renal insufficiency) will be obtained at the 6 and 12 month visits. At each visit, patients will be assessed for Head and Neck toxicity using the Common Terminology Criteria for Adverse Events (CTCAE) version 4.0. While no other toxicities are expected, any additional toxicity should also be scored by CTCAE version 4.0. In addition they will complete the FACT-H&N questionnaire (validated questionnaires to assess treatment related quality of life). When study follow-up is completed at 12 months, the patient will transition to standard follow-up off protocol with physician visits and head and neck exam every 3 months for year 2, every 4 months for year 3, every 6 months for year 4 and annually thereafter.

7.0 DOSING DELAYS / DOSE MODIFICATIONS

7.1 Modifications to the treatment schedule due to changes in patient condition are at the discretion of the treating physician. Such modifications are not expected as the expected acute toxicity of the treatment is minimal. If any patient requires dosing delay such that the total duration of the radiation course is greater than 18 days due to a clinical factor this will be reported.

7.2 There will be no dosing modifications made to the three predefined dosing cohorts. Accrual to the predefined dose cohorts will be performed according to Section 3.1.

8.0 ADVERSE EVENTS: LIST AND REPORTING REQUIREMENTS

The following is a list of AEs (Section 8.1) and the reporting requirements associated with observed AEs (Sections 8.3 and 8.4).

Adverse events will be followed until resolution or for a maximum of 30 days post study discontinuation. Serious adverse events that are still ongoing at the end of the study period will necessitate further follow-up to determine the final outcome.

8.1 Adverse Events and Potential Risks

8.1.1 SBRT

Treatment related head and neck toxicity will be monitored using the CTCAE version 4.0 instrument. Toxicity data will be continually assessed by the treating radiation oncologist each time a patient comes for a clinical visit, and the data will be entered into the database. Excessive toxicity that would lead to termination of the study includes the requisite number of grade 4 or 5 toxicities as detailed in 3.0 above.

8.2 Definitions

8.2.1 Adverse Events

An **adverse event** (AE) is any unfavorable or unintended event, physical or psychological, associated with a research study, which causes harm or injury to a research participant as a result of the participant's involvement in a research study. The event can include abnormal laboratory findings, symptoms, or disease associated with the research study. The event does not necessarily have to have a causal relationship with the research, any risk associated with the research, the research intervention, or the research assessments.

Adverse events may be the result of the interventions and interactions used in the research; the collection of identifiable private information in the research; an underlying disease, disorder, or condition of the subject; and/or other circumstances unrelated to the research or any underlying disease, disorder, or condition of the subject. In general, adverse events that are at least partially the result of (a) or (b) would be considered related to the research, whereas adverse events solely related to (c) or (d) would be considered unrelated to the research.

8.2.2 The significance of an adverse event is used to describe the patient/event outcome or action criteria associated with events that pose a threat to a patient's life or functioning (i.e., moderate, severe or life threatening). Based on the National Cancer Institute Guidelines for the Cancer Therapy Evaluation Program, severity can be defined by the following grades of events:

Grades 1 are mild adverse events. (e.g., minor event requiring no specific medical intervention; asymptomatic laboratory findings only; marginal clinical relevance)

Grades 2 are moderate adverse events (e.g., minimal intervention; local intervention; non-invasive intervention or elective interventional radiological procedure; transfusion;).

Grades 3 are severe and undesirable adverse events (e.g., significant symptoms requiring hospitalization or invasive intervention; transfusion; therapeutic endoscopy or operation).

Grades 4 are life threatening or disabling adverse events (e.g., complicated by acute, life-threatening metabolic or cardiovascular complications such as circulatory failure, hemorrhage, sepsis; life-threatening physiologic consequences; need for intensive care or

emergent invasive procedure; emergent interventional radiological procedure, therapeutic endoscopy or operation).

Grades 5 are fatal adverse event resulting in death.

8.2.3 Serious Adverse Events

A **serious adverse event** (SAE) is any adverse experience occurring at any dose that results in any of the following outcomes:

- Results in **death**.
- Is a **life-threatening** adverse experience. The term life-threatening in the definition of serious refers to an adverse event in which the subject was at risk of death at the time of the event. It does not refer to an adverse event which hypothetically might have caused death if it were more severe.
- Requires **inpatient hospitalization or prolongation of existing hospitalization**. Any adverse event leading to hospitalization or prolongation of hospitalization will be considered as Serious, UNLESS at least one of the following expectations is met:
 - The admission results in a hospital stay of less than 12 hours OR
 - The admission is pre-planned (i.e., elective or scheduled surgery arranged prior to the start of the study) OR
 - The admission is not associated with an adverse event (e.g., social hospitalization for purposes of respite care).

However it should be noted that invasive treatment during any hospitalization may fulfill the criteria of “medically important” and as such may be reportable as a serious adverse event dependant on clinical judgment. In addition where local regulatory authorities specifically require a more stringent definition, the local regulation takes precedent.

- Results in **persistent or significant disability/incapacity**. The definition of disability is a substantial disruption of a person’s ability to conduct normal life’s functions.
- Is a **congenital anomaly/birth defect**.
- Is an **important medical event**. Important medical events that may not result death, be life-threatening, or require hospitalization may be considered a serious adverse experience when, based upon appropriate medical judgment, they may jeopardize the patient or subject and may require medical or surgical intervention to prevent one of the outcomes listed in this definition. Examples of such medical events include allergic bronchospasm requiring intensive treatment in an emergency room or at home, blood disease or disorders, or convulsions that do not result in inpatient hospitalization, or the development of drug dependency or drug abuse.

8.2.4 Expectedness

Adverse Events can be Expected or Unexpected.

An expected adverse event is an event previously known or anticipated to result from participation in the research study or any underlying disease, disorder, or condition of the subject.

An unexpected adverse event is an adverse event not previously known or anticipated to result from the research study or any underlying disease, disorder, or condition of the subject.

8.2.5 Attribution

Attribution is the relationship between an adverse event or serious adverse event and the study drug. Attribution will be assigned as follows:

- Definite – The AE is clearly related to the study drug/procedure.
- Probable – The AE is likely related to the study drug/procedure.
- Possible – The AE may be related to the study drug/procedure.
- Unlikely – The AE is doubtfully related to the study drug/procedure.
- Unrelated – The AE is clearly NOT related to the study drug/procedure.

8.3 Reporting Procedures for All Adverse Events

All participating investigators will assess the occurrence of any treatment related AEs throughout the subject's participation in the study. Subjects will be followed for toxicity one year after treatment has been discontinued or until death, whichever occurs first. The clinical course of each event will be followed until resolution, stabilization, or until it has been determined that the study treatment or participation is not the cause.

The investigator is responsible for ensuring that all treatment related AEs observed by the investigator or reported by the subject which occur after the subject has signed the informed consent are fully recorded in the subject's case report form, subject's medical records, and/or any other institutional requirement. Source documentation must be available to support all adverse events.

A laboratory test abnormality considered clinically relevant (e.g., causing the subject to withdraw from the study), requiring treatment or causing apparent clinical manifestations, or judged relevant by the investigator, should be reported as an adverse event.

The study team will provide the following for all adverse events:

- Description of the event
- Date of onset and resolution
- Grade of toxicity
- Attribution of relatedness to the investigational agent
- Action taken as a result of the event
- Outcome of event

In this study, descriptions and grading scales found in the NCI Common Terminology Criteria for Adverse Events (CTCAE) version 4.0 available at <http://ctep.cancer.gov> will be utilized for

AE reporting.

Adverse events will be reported to the IRB according to the IRB policies and procedures in reporting adverse events.

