8.4 Serious Adverse Event Reporting Procedures

Serious adverse events that occur beginning with the signing of the informed consent form, during treatment, or within thirty days of the last dose of treatment must be reported to the Cleveland Clinic Principal Investigator.

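### Section 8.3 limits AE assessment and case report form entry to treatment-related events, against the AE definition, the attribution scale and its own later sentences

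*Combined protocol and SAP*

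**What the plan says.** Two sentences in section 8.3 set the operative duties, and both carry a causality condition. On assessment: "All participating investigators will assess the occurrence of any treatment related AEs throughout the subject's participation in the study". On recording, the investigator is responsible for "ensuring that all treatment related AEs observed by the investigator or reported by the subject" after consent being fully entered in the case report form, the medical records or both.

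The same section then drops the condition. It states "Source documentation must be available to support all adverse events", and it introduces a list of data items, among them grade and attribution, with "The study team will provide the following for all adverse events".

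The definitions are wider than the recording duty. Section 8.2.1 says "The event does not necessarily have to have a causal relationship with the research" and counts events arising from underlying disease as AEs. Section 8.2.5 has five attribution levels, the lowest being "The AE is clearly NOT related to the study drug/procedure".

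Serious events have their own route. Under section 8.4, those occurring from consent, during treatment, or "within thirty days of the last dose of treatment must be reported to the Cleveland Clinic Principal Investigator". Section 8.5 requires all SAEs to go to the Data Safety Toxicity Committee and gives no time limit. Neither section has an attribution condition.

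**The concern.** Attribution should be a judgement recorded about an event, open to later revision. Under the two duty sentences of 8.3 it becomes a condition for entering the event at all. A wrong judgement of unrelatedness then leaves nothing in the case report form to revisit.

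This matters because safety is the main endpoint and section 3.1.6 calls the treatment novel in this population. Patients may enter with a Karnofsky score as low as 40, and section 1.2 describes a population unfit for standard treatment partly through age and comorbidity. Their events are easily put down to background illness. Objective 2.2.1 asks for toxicity profiles and for factors, including comorbidities, associated with SBRT-related toxicity. If comorbidity makes an event likelier to be called unrelated, the filter removes the observations that the analysis needs.

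**Working it through.** The point rests on wording, so the check sets the sections side by side and traces which events have a recording route that does not depend on attribution.

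**Step 1: which events must be recorded.**
- 8.3, assessment duty: treatment-related only.
- 8.3, case report form duty: treatment-related only.
- 8.3, heading, source documents and data items: all AEs.
- 8.2.1, later sentence: AEs irrespective of cause. Its opening sentence points the other way, describing an event "which causes harm or injury to a research participant as a result of the participant's involvement in a research study".
- 8.2.5: unlikely and unrelated are levels to be assigned, and they have little use if such events are not entered.

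Section 8.3 therefore contradicts itself as well as 8.2.5 and the later sentence of 8.2.1. A site could follow either reading and claim compliance.

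**Step 2: which events have another route.**
- *Serious, up to 30 days after the last dose:* 8.4 to the principal investigator and 8.5 to the committee, both without regard to attribution. Covered.
- *Serious, after 30 days:* 8.5 still says all, but the duty in 8.4 has ended and no other stated step brings the event to the principal investigator. Case report form entry falls under the filtered sentence of 8.3. Unclear.
- *Non-serious:* no SAE route. Section 6.4 scores head and neck toxicity and any additional toxicity by CTCAE at each visit, but does not say that this holds irrespective of cause, and 8.1.1 describes the monitoring as of treatment-related toxicity. Exposed.

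**Step 3: how much follow-up lies beyond 30 days.** Sections 3.3.2 and 6.4 schedule visits at 0.5, 3, 6, 9 and 12 months. Only the 0.5-month visit falls within 30 days, so 5 − 1 = 4 of the 5 fall outside the 8.4 window. Section 3.1.3 assesses DLTs at 3 months, and 3.1.5 says they can occur later.

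**Step 4: whether the escalation figures move.** The only computed design figures are in the section 12 table, where

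P(next dose) = P(X ≤ 1 of 6) + P(X = 2 of 6) × P(X ≤ 1 of second 6).

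At a DLT probability of 0.30 this is 0.4202 + 0.3241 × 0.4202 = 0.5564, against the stated 0.56. The other rows also reproduce: 0.913, 0.816, 0.692 and 0.306 against 0.91, 0.82, 0.69 and 0.31. The DLT count that drives the rule is governed by 3.1.6, which lists grade 4/5 events, and by 3.1.8, which removes those attributed to progression. Section 8.3 is not part of that rule, and correcting it changes no figure in the table.

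**The case against.** The strongest reply is that 8.3, read whole, does not exclude unrelated events. It asks for source documents and attribution for every AE, requires clinically relevant laboratory abnormalities to be reported without a causality condition, and follows each event until treatment has been ruled out as the cause, which presupposes that events are captured first. This stands in part: it shows an inconsistency, not a clear exclusion rule. It does not cure the defect, because the sentence assigning responsibility for case report form entry is the one with the filter.

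A second reply is that serious events are protected. Section 8.2.3 defines an SAE by outcome, 8.4 and 8.5 apply whatever the attribution, and 3.1.7 records all grade 3 toxicities as SAEs. This stands for the first 30 days. A reader might infer that unrelated events vanish before the committee or anyone else can see them; for serious events the documents do not support that. After 30 days, 8.4 and 8.5 do not agree on a route.

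A third reply is that 3.1.8 requires the treating physician and another co-investigator before morbidity attributed to progression is set aside. This also stands, but it covers progression only, not comorbidity, and it governs dosing decisions, not data entry.

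A reader might also infer that under-recording raises the chance of escalating at a toxic dose. That needs an assumed share of DLTs lost through 8.3, and the documents give none. Grade 4/5 events are nearly all SAEs under 8.2.3, and they are counted under 3.1.6 and 3.1.8.

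**Conclusion.** The contradiction is real and can be seen from the text alone. Followed literally, the duty sentences of 8.3 let events judged unrelated go unrecorded. The clear exposure is non-serious events, plus serious events more than 30 days after the last dose.

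The likely direction is downward, for the toxicity profile and for the comorbidity associations in objective 2.2.1. Events correctly judged unrelated would not belong in an analysis of SBRT-related toxicity anyway. The harm comes from related events misjudged as unrelated, and it assumes that some occur and that sites follow the narrow wording. The documents give no rate for either, so no numerical size can be stated. The section 12 escalation probabilities are not shown to be affected.

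**What to change.** - In both duty sentences of 8.3, replace the restriction to treatment-related events with *all AEs regardless of attribution*.
- State that the 8.2.5 attribution is assigned after the event is recorded.
- In section 12, specify toxicity tables for all AEs and for those rated at least possibly related.
- Remove the causal wording from the first sentence of 8.2.1, so that it agrees with the rest of that section.
- Reconcile the 30-day reporting window in 8.4 with 8.5 and with the one-year toxicity follow-up in 6.4 and 8.3.

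The cost is an amendment to wording and some additional AE entries, in a trial with a planned maximum of 18 patients (section 3.2). The DLT definition, the escalation rule and the section 12 probabilities stay as they are.

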8.4 Serious Adverse Event Reporting Procedures

Serious adverse events that occur beginning with the signing of the informed consent form, during treatment, or within thirty days of the last dose of treatment must be reported to the Cleveland Clinic Principal Investigator.

8.5 Data Safety Toxicity Committee

It is the Case Comprehensive Cancer Center's Principal Investigator's responsibility to ensure that ALL serious adverse events are reported to the Case Comprehensive Cancer Center's Data Safety Toxicity Committee. This submission is simultaneous with their submission to the Sponsor or other Regulatory body.

9.0 STUDY PARAMETERS AND CALENDAR

9.1 Study Parameters

9.1.1 Screening Evaluation

Patients will complete the FACT H&N quality of life questionnaires at baseline.

9.2 Calendar

Assessment	Months Since Treatment					
	Baseline	0 Post Treatment (Last OTR Visit)	0.5 (1-3wks)	3	9	6, 12
Informed Consent	X					
Medical History	X					
Vitals ¹	X	X	X	X	X	X
Physical Exam ²	X	X	X	X	X	X
PET/CT ³	X			X		
CT neck and chest ⁴						X
FACT-H&N survey	X		X	X	X	X
CTCAE Toxicity Assessment		X	X	X	X	X

¹ Height not required

² Focused head and neck exam at each visit with optional pharyngolaryngoscopy

³ An additional PET/CT may be done after the 3 month time point to help clarify the etiology of abnormalities that are found clinically or radiographically to suggest potential recurrence/progression

⁴ With contrast unless contraindicated

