Dose limiting toxicities in this study will be defined as grade 4/5 toxicity:

- soft tissue or bone necrosis
- carotid blowout or other treatment related bleed
- aspiration
- infection
- fistula that is deemed as life threatening.

While grade 3 toxicities will be recorded as SAEs and reported as per IRB guidelines, they will not be considered DLTs or influence the dose escalation component of the study, given the high risk nature of the disease and the associated morbidities of uncontrolled disease.

3.1.7 All grade 3 toxicities will be recorded as serious adverse events but will not be scored as DLT, as these are somewhat expected and most often reversible complications associated with radiotherapy. Grade 1/2 events will be recorded, but will not be considered serious adverse events.

3.1.8 Symptoms and morbidity attributed to disease progression, as determined by the treating physician, and another co-investigator of the study, will not be considered a toxicity that will influence the dosing schema.

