H&N1	I am able to eat the foods that I like	0	1	2	3	4
H&N2	My mouth is dry	0	1	2	3	4
H&N3	I have trouble breathing.....	0	1	2	3	4
H&N4	My voice has its usual quality and strength.....	0	1	2	3	4
H&N5	I am able to eat as much food as I want	0	1	2	3	4
H&N6	I am unhappy with how my face and neck look.....	0	1	2	3	4
H&N7	I can swallow naturally and easily.....	0	1	2	3	4
H&N8	I smoke cigarettes or other tobacco products	0	1	2	3	4
H&N9	I drink alcohol (e.g. beer, wine, etc.).....	0	1	2	3	4
H&N ₁₀	I am able to communicate with others.....	0	1	2	3	4
H&N ₁₁	I can eat solid foods.....	0	1	2	3	4
H&N ₁₂	I have pain in my mouth, throat or neck.....	0	1	2	3	4

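### No CTCAE grade is scheduled before SBRT, so grade 1-3 symptoms present at entry can be told apart from SBRT toxicity only by investigator attribution

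*Combined protocol and SAP*

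**What the plan says.** In the section 9.2 calendar, the row "CTCAE Toxicity Assessment" has marks at the last on-treatment visit and at 0.5, 3, 9 and 6/12 months. Its baseline cell is empty. Medical history, vitals, physical exam, PET/CT and FACT-H&N are all marked at baseline, and a footnote specifies "Focused head and neck exam at each visit with optional pharyngolaryngoscopy".

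Three other places bear on timing:

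- Section 6.4: "At each visit, patients will be assessed for Head and Neck toxicity using the Common Terminology Criteria for Adverse Events (CTCAE) version 4.0". This follows a list of post-SBRT visits only.
- Section 8.1.1: "Toxicity data will be continually assessed by the treating radiation oncologist each time a patient comes for a clinical visit". The paragraph concerns treatment-related toxicity and does not ask for a pre-treatment grade.
- Section 9.1.1, the screening evaluation, names one assessment: "Patients will complete the FACT H&N quality of life questionnaires at baseline".

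On the events themselves, section 3.1.6 states "Dose limiting toxicities in this study will be defined as grade 4/5 toxicity", followed by a short list: necrosis, carotid blowout or treatment-related bleeding, aspiration, infection, and life-threatening fistula. Section 3.1.7 records every grade 3 toxicity as a serious adverse event. Section 3.1.8 removes from the dosing decision any morbidity that two study physicians put down to disease progression.

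**The concern.** Inclusion criterion 4.1.3 requires a primary tumour or node of at least 2.5 cm, and 4.1.6 admits a Karnofsky score as low as 40. Some patients will plausibly arrive with trouble swallowing, pain or other symptoms that CTCAE would grade. Exclusion 4.2.6 bars earlier head and neck radiotherapy only above 40 Gy with significant overlap, so some may also carry earlier radiation effects.

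Response is measured against a baseline sum of diameters (10.1), and quality of life has a baseline questionnaire. Safety, the primary endpoint, has no baseline on its own scale, and nothing in the plan defines toxicity as worsening from the entry state.

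What is at stake is mainly secondary. Objectives 2.2.1 and 2.2.2 ask which patient, tumour, treatment and dose-volume factors go with SBRT toxicity, and section 12 applies Mann-Whitney and Fisher tests to DLTs and to grade 3 acute and late events. If entry symptoms are counted as toxicity, the error need not be random. Section 6.2 builds the PTV as a 2-3.5 mm expansion of the gross tumour, so treated volume grows with tumour size. If symptoms at entry also grow with tumour size, a dose-volume association can appear that treatment did not cause.

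**Working it through.** **1. Is there a pre-SBRT grade anywhere?** The calendar has six visit columns and the CTCAE row has five marks; the one without a mark is baseline. Section 6.4 covers follow-up visits and 9.1.1 names FACT-H&N only. Section 8.1.1 covers treatment-related toxicity. Section 8.3 requires recording of treatment-related events arising after consent, so a symptom already present at consent falls outside it. The answer is no.

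**2. What else can separate entry symptoms from toxicity?**

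| Source | What it gives | What it lacks |
|---|---|---|
| 9.2 baseline history, exam, PET/CT | Written pre-treatment record | A grade |
| FACT-H&N, for example "I can swallow naturally and easily" | Patient score 0-4 | Not a CTCAE grade |
| 8.2.1 | Events due solely to underlying disease count as unrelated | A reference value |
| 8.2.5 and 8.3 | Five-level attribution, onset date, grade, source documents | A reference value |
| 3.1.8 | Two-physician exclusion for progression | Silent on a symptom present at entry that persists without progression |

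Separation is possible, but by judgement and without a same-scale reference.

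**3. Weight of one patient.** With the planned maximum of 18 (section 3.2), 1/18 = 5.6 percentage points. In a cohort of six (3.1.2), 1/6 = 16.7 points.

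The documents give no prevalence of entry symptoms. If 10-20% of patients entered with a grade 3 symptom (assumption), 0.10 × 18 = 1.8 to 0.20 × 18 = 3.6 patients would be open to misattribution. That is a ceiling, reached only if attribution never works.

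**4. The dose-escalation figures.** Section 12 tabulates the probability of escalating. With X the number of DLTs in six patients at true rate p:

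P(escalate) = P(X ≤ 1) + P(X = 2) × P(X ≤ 1)

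- p = 0.15: 0.7765 + 0.1762 × 0.7765 = 0.913 (plan 0.91)
- p = 0.30: 0.4202 + 0.3241 × 0.4202 = 0.556 (plan 0.56)
- p = 0.20, 0.25, 0.40: 0.816, 0.692, 0.306 (plan 0.82, 0.69, 0.31)

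All five reproduce. None depends on baseline grading, so the fix changes none of them.

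**5. How sensitive the six-patient rule would be.** The misattribution rates below are assumptions.

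- *False DLTs.* A share b of patients without a true DLT is scored as having one, so the apparent rate is p + (1 − p)b. At p = 0.15 and b = 10%: 0.15 + 0.85 × 0.10 = 0.235, and P(escalate) = 0.5699 + 0.2837 × 0.5699 = 0.73. For b = 0, 5, 10, 15, 20% the results are 0.91, 0.83, 0.73, 0.62, 0.50.
- *Missed DLTs.* A share f of true DLTs is put down to the tumour, so the apparent rate is p(1 − f). At p = 0.30 and f = 20%: 0.30 × 0.80 = 0.24, and P(escalate) = 0.5578 + 0.2883 × 0.5578 = 0.72. For f = 0, 10, 20, 30, 50% the results are 0.56, 0.64, 0.72, 0.79, 0.91.

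These show that the rule reacts to misattribution. They do not show that misattribution at grade 4/5 is likely.

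**The case against.** The strongest reply is that the plan already handles this through attribution. Section 8.2.1 lists the subject's underlying disease as a source of adverse events and treats events due solely to it as unrelated. The letters it refers to are not printed, but the order of the list identifies it. That wording reaches symptoms present at entry, not only progression. Sections 8.2.5 and 8.3 then require graded attribution, onset dates and source documents, and the objectives and section 12 restrict the analyses to SBRT-related events.

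Much of this stands. A reader might infer from the blank cell that disease symptoms and SBRT toxicity cannot be told apart at all, or that attribution rests on memory. The documents do not support either: there is a written pre-treatment history, exam, scan and questionnaire.

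A reader might also infer that dose decisions are compromised. That is not supported either. Only listed grade 4/5 events count, dysphagia is not listed, non-carotid bleeding must be treatment related and fistula must be life threatening. A fatal event cannot pre-date treatment, and life expectancy under six months is an exclusion. The opening that remains is that aspiration and infection carry no relatedness wording in the DLT list.

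What the reply does not answer is that attribution is a judgement with no recorded grade to check it against. For grade 1-3 symptoms in this population, that judgement decides what enters the toxicity profile.

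**Conclusion.** The point holds for the toxicity profile, the factor and dose-volume associations, and the grade 3 analyses. Followed as written, the plan collects no pre-SBRT grade on the safety scale, so change from baseline cannot be reported and the handling of entry symptoms cannot be audited on that scale. The possible bias has a plausible direction, towards larger tumours appearing more toxic. That rests on the assumption that larger tumours bring more symptoms at entry, on which the documents give no data.

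Its size is unknown. Each misattributed patient is worth 5.6 points among 18, or 16.7 points among six. It would be wrong to read the ceiling of about 2 to 4 patients as the number who will be misclassified: the prevalence behind it is assumed, and it supposes that attribution fails every time. The effect on grade 4/5 DLTs is probably small, which is a judgement since no rate is given. No figure in section 12 is in error on this account.

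This should be changed, because the visit already takes place and ungraded baselines can be only partly reconstructed later.

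**What to change.** - Section 9.2: add a mark for CTCAE assessment in the Baseline column, with a matching line in 9.1.1.
- Section 12: for each CTCAE term, report both the worst post-SBRT grade and the change from the baseline grade.
- Section 8.3: state that the baseline grade informs attribution, including for symptoms present at entry that persist without progression.

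The baseline grade should not be an automatic filter. Counting an event only when it exceeds the entry grade would drop a new SBRT-caused infection or aspiration of the same grade as an earlier one, or a symptom that resolved and came back because of treatment. In a study whose primary endpoint is safety, that would undercount toxicity.

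The cost is a few minutes of grading at an existing visit and one added CRF field. The sample size, the escalation rule and the probabilities in section 12 are unaffected. For patients already treated, a grade derived from the baseline history, exam and FACT-H&N would be only a partial substitute and should be labelled retrospective.
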